The goal of this study is to assess safety of treating patients with metastatic prostate cancer with MRI-guided prostate SBRT. Safety is defined as lack of more than 3 patients with treatment related acute >G3 GI or GU toxicity within 3- 6 months post treatment. The proposed SBRT dose (36.25 Gy in 5 fractions to the whole prostate) has been reported in the literature to be safe and well tolerated (Table 2), with no acute G3 toxicity. The proposed boost dose to 40 Gy in applicable patients is within the range of current standard of care SBRT doses, and is also expected to be well-tolerated. Furthermore, it has been tested in our currently ongoing investigator initiated protocol in patients with non-metastatic prostate cancer (“MRI-guided Stereotactic Body Radiotherapy (SBRT) with Simultaneous Integrated Boost for Prostate Cancer” PI: [name], [name] IRB Protocol # 1802019010). As of 4/29/19, 15 patients with localized prostate cancer have enrolled on this study with planned accrual of 30 patients, and have demonstrated excellent safety and feasibility with boost doses up to 45 Gy. It

is therefore expected that similar outcomes can be achieved in patients with metastatic prostate cancer, though it is possible that the addition of systemic therapy may alter likelihood of toxicity.

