10 MEASUREMENT OF EFFECT

This is a safety study.

Treatment will be deemed safe if there are no more than 3 acute greater than grade 3 radiation treatment related GI/GU adverse events within 3-6 months of treatment (CTCAE 5.0 criteria).

The primary endpoint will be safety, as measured by the percentage of treatments that are delivered without radiation treatment related GI/GU toxicity within 3-6 months from start of treatment. Given that the treatment plans will meet standard normal tissue constraints used for SBRT, and rigorous safety metrics need to be met before radiation is delivered, we do not anticipate any increased toxicity on this study compared to standard SBRT.

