12.1.1 Primary Objectives

Safety of this approach will be determined by assessing acute GI/GU toxicity (CTCAE 5). The treatment will be deemed safe if no more than 3 patients experience a grade 4 likely radiation treatment related GI/GU (or higher) adverse event within 3-6 months from the end of treatment.

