12.1.3 Correlative Study Objectives

Microbiome and labs will be collected for exploratory analyses to see how radiation impacts the host microbiome and peripheral immune correlates found in blood.

12.2 *Sample Size/Accrual Rate*

We plan to accrue 20 patients over 2 years, or about 4-6 patients every 6 months.

12.3 *Analysis of Primary and Secondary Endpoints*

Primary Endpoint:

The treatment will be deemed safe if the grade 4+ likely radiation treatment related GI/GU adverse event rate is less than 10% within 3-6 months of the end of treatment. The proportion of patients that experience a >grade 3 GU/GU adverse event will be determined with a binomial

point estimate and corresponding exact 95% binomial confidence interval. If the lower bound of the interval is below 10%, the treatment will be considered safe.

Secondary Endpoints:

QOL measures at baseline and at follow up (3-6 months post treatment start, and 9-12 months) will be summarized numerically and graphically using mean (sd), median (interquartile range), or count (percent) as appropriate, and 95% confidence intervals estimated where possible. The QOL value will be plotted over time with a line for each patient and a smoothed curve superimposed on the plot. Changes in scoring from pre- to post-treatment will also be determined. EPIC-26 overall scores as well as domain summary scores (urinary incontinence, urinary irritative/obstructive, bowel, sexual, hormonal) and individual item responses will be evaluated. Similarly, overall score as well as individual item responses will be assessed for the I-PSS survey.

Toxicity will be assessed using CTCAE 5.0 criteria at 3-6 months and 9-12 months.

These analyses will be descriptive.

Correlative study endpoints:

Microbiome

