13.2 Stopping rules

If more than 2 patients experience a grade 4 likely radiation treatment related adverse event, the study will suspend accrual and the study team will evaluate the adverse events to determine whether they were at least possibly related to treatment. A decision will be made with approval of the DSMB to either modify the protocol or to terminate the trial due to an unacceptable adverse event rate.

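### Sections 12.1.1 and 12.3 give final safety rules that disagree, no text says which governs, and the lower-bound rule in 12.3 is wrong as written

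*Combined protocol and SAP*

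**What the plan says.** Three final rules appear in current text.

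- **Count.** Section 12.1.1: "The treatment will be deemed safe if no more than 3 patients experience a grade 4 likely radiation treatment related GI/GU", extended there to higher grades, within the 3-6 month window. Section 2.7 has the same limit: "Safety is defined as lack of more than 3 patients with treatment related acute >G3 GI or GU toxicity". The Protocol Summary and section 1.1 also use a limit of 3, without saying whether patients or events are counted. Section 10 counts events: "no more than 3 acute greater than grade 3 radiation treatment related GI/GU adverse events".
- **Rate.** Section 12.3, primary endpoint: "The treatment will be deemed safe if the grade 4+ likely radiation treatment related GI/GU adverse event rate is less than 10" per cent.
- **Interval.** Later in the same paragraph, after specifying an exact 95% binomial interval: "If the lower bound of the interval is below 10%, the treatment will be considered safe".

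Separately, section 13.2 sets a monitoring rule: "If more than 2 patients experience a grade 4 likely radiation treatment related adverse event, the study will suspend accrual". The study team then reviews relatedness, and a decision is taken with DSMB approval "to either modify the protocol or to terminate the trial due to an unacceptable adverse event rate".

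Planned enrolment is 20 (section 12.2), with an accrual ceiling of 25 (Protocol Summary). The summary of changes for version 5.0 records that accrual is closed and patients are in follow-up.

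**The concern.** This is a single-arm safety study, so the safety verdict is its primary result. If the count, the rate and the interval bound put the line in different places and none is named as governing, then over a range of outcomes the report could say safe or not safe and cite the plan correctly for either. With accrual closed, that reported conclusion is the main decision still open.

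The interval rule has a second problem. A lower confidence bound below 10% means only that the data do not rule out a rate below 10%. It is not evidence that the rate is below 10%, and with 20 to 25 patients the bound stays under 10% at observed rates of about a quarter.

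**Working it through.** The plan gives no error rates, design rates or power for its sample size, so there is no stated figure to reproduce. The check applies each written rule to every possible count.

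**Inputs.** n = 20 (section 12.2) and n = 25 (Protocol Summary); limit of 3 patients (12.1.1); 10% threshold and exact two-sided 95% interval (12.3).

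**Formulas.** Observed rate = x/n. Exact lower bound = the 0.025 quantile of Beta(x, n − x + 1). Probability of a safe verdict = P(X ≤ c), with X binomial(n, p) and c the largest count the rule calls safe.

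**Step 1: verdict by count.**

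| n | x | x/n | Exact lower bound | Count ≤ 3 | Rate < 10% | Lower bound < 10% |
|---|---|---|---|---|---|---|
| 20 | 1 | 5% | 0.1% | safe | safe | safe |
| 20 | 2 | 10% | 1.2% | safe | not | safe |
| 20 | 3 | 15% | 3.2% | safe | not | safe |
| 20 | 4 | 20% | 5.7% | not | not | safe |
| 20 | 5 | 25% | 8.7% | not | not | safe |
| 20 | 6 | 30% | 11.9% | not | not | not |
| 25 | 2 | 8% | 1.0% | safe | safe | safe |
| 25 | 3 | 12% | 2.55% | safe | not | safe |
| 25 | 4 | 16% | 4.5% | not | not | safe |
| 25 | 6 | 24% | 9.4% | not | not | safe |
| 25 | 7 | 28% | 12.1% | not | not | not |

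The largest safe counts are therefore 3, 1 and 5 at n = 20, and 3, 2 and 6 at n = 25. The ratio 3/n first falls below 10% at n = 31 (3/31 = 9.7%), so no permitted sample size reconciles the count with the observed-rate rule.

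**Step 2: the other reading of 12.3.** Suppose the first sentence states a target for the true rate and the interval sentence is its only test. Then 12.3 says safe at 3 patients, as 12.1.1 does. The two sections then conflict at 4-5 of 20 and 4-6 of 25.

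**Step 3: how often it matters.** The true rates are assumptions, because the documents give no acute grade 4+ rate.

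| True rate | Two rules in 12.3 disagree, n = 20 (x = 2-5) | Same, n = 25 (x = 3-6) | Count and lower bound disagree, n = 20 (x = 4-5) | Same, n = 25 (x = 4-6) |
|---|---|---|---|---|
| 1% | 1.7% | 0.2% | <0.1% | <0.1% |
| 2% | 6.0% | 1.3% | 0.1% | 0.1% |
| 3% | 12.0% | 3.8% | 0.3% | 0.6% |
| 5% | 26.4% | 12.7% | 1.6% | 3.4% |
| 10% | 59.7% | 45.3% | 12.2% | 22.7% |

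The last two columns are differences of cumulative probabilities. For example, at n = 20 and 10%: P(X ≤ 5) − P(X ≤ 3) = 0.9887 − 0.8670 = 0.1217.

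**Step 4: what each rule lets through.** At n = 20 and a true rate of 20%, twice the threshold, the chance of a safe verdict is P(X ≤ 1) = 6.9% under the rate rule, P(X ≤ 3) = 41.1% under the count, and P(X ≤ 5) = 80.4% under the lower bound.

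**The case against.** **12.3 may contain one rule, not two.** Its interval sentence can be read as the test of the 10% target. The text does not exclude this, so it cannot be said flatly that 12.3 gives both answers at 3 patients. But the reading only moves the conflict to 4-5 of 20 or 4-6 of 25, and it makes the weakest rule the operative one.

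**The disputed counts are unlikely.** Section 2.7 says of the planned dose that it "has been reported in the literature to be safe and well tolerated (Table 2), with no acute G3 toxicity", and Table 2 lists grade 3 or higher toxicity of 0% to 4.4% per organ. Section 2.4 presents those as late toxicity, so they bear only indirectly on acute grade 4 events, but low rates remain the more plausible ones. This stands and limits the size of the problem. Even so, a safety rule has to work when toxicity exceeds expectation, and section 2.7 itself allows that systemic therapy may change the risk.

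**A reader might infer that 13.2 contradicts 12.1.1**, so that the plan calls 3 patients both safe and unacceptable. The documents do not support that. Section 13.2 suspends accrual for review. It includes a relatedness check, needs DSMB approval and allows modification; the words about an unacceptable rate attach to termination. Its scope also differs: grade 4 only, any organ, no time window. An interim trigger may properly be stricter than the final criterion.

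**A reader might also infer that the final limit must drop to 2.** No stated final rule uses 2 at n = 20, since 2/20 = 10% is not below 10%. Tightening the criterion after accrual closed could look data-driven. At n = 20 and a true 5%, it would cut the chance of a safe verdict from 98.4% to 92.5%.

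**Conclusion.** The concern holds for sections 12.1.1 and 12.3. They set final safety rules with different limits and name none as governing, and on either reading of 12.3 some counts get opposite verdicts. The lower-bound sentence is an error in its own right: it would accept 5/20 (25%) or 6/25 (24%) as safe.

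The verdicts by count follow from the text and exact binomial arithmetic alone. The frequencies rest on assumed true rates. At 1% to 3%, the practical chance of conflict at n = 20 is 1.7% to 12.0% if the 10% rule means the observed rate, and at most 0.3% if the interval is the only test. Both rise steeply at higher rates. Actual enrolment is not stated, so 20 and 25 are used as the planned size and the ceiling. The finding does not extend to 13.2 as a contradictory verdict and does not require a limit of 2. It should be settled before the primary result is reported.

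**What to change.** 1. In 12.3, delete the sentence that bases the verdict on the lower bound. Keep the point estimate and exact 95% interval as description. Swapping in the upper bound would not work: with zero events it is already 16.8% at n = 20 and 13.7% at n = 25.
2. State that the 12.1.1 criterion alone sets the conclusion: no more than 3 patients with a grade 4 or higher, likely radiation-related GI/GU event in the window. Remove the 10% verdict from 12.3 or restate it to match, since 3/20 = 15% and 3/25 = 12%. Report the observed rate and interval beside the verdict, so that readers can see what a count of 3 means.
3. Make the Protocol Summary, section 1.1 and section 10 count patients. Section 10 also describes the endpoint as a percentage of treatments free of GI/GU toxicity, with no grade and timed from the start of treatment. Counting patients does not settle that wording, which should be aligned separately.
4. In 13.2, write grade 4 or higher and state that the section is a monitoring trigger only.
5. Date the amendment and state whether event counts were known when it was written.

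Lowering the limit to 2 is open to the sponsor as a choice but is not a required correction.

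The cost is a wording amendment. The safe verdict is no longer available at 4-5 of 20 or 4-6 of 25.
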